4.2.3. Per protocol set

The per protocol (PP) population: All randomized subjects who completed participation in the study in accordance with the protocol (have completed the prescribed period of treatment and follow-up without significant deviations from the protocol).

5. Demographics and baseline characteristics

All the data obtained in the groups before the study therapy initiation (demographic, laboratory, instrumental, and physical examinations data, vital signs, etc.) will be compared to determine the groups' comparability for analysis.

For quantitative characteristics, it is planned to calculate the following statistics:

- 1) Quantity
- 2) Number of missing values
- 3) Median
- 4) 95% CI for the mean
- 5) Standard deviation
- 6) Median
- 7) Minimum
- 8) Maximum
- 9) First quartile
- 10) Third quartile
- 11) Interquartile range

For categorical variables, it is planned to calculate the following characteristics:

- 1) Absolute number by the group
- 2) Percentage relative to groups

3) Percentage of visits by group

Quantitative variables will be checked for compliance with the normal distribution using the Shapiro–Wilk test.

To compare quantitative data distributed according to the normal distribution, it is planned to use parametric criteria: Student's t-test for dependent/independent samples, analysis of variance (ANOVA) for repeated measurements to compare more than two stages.

To compare quantitative data distributed according to a principle other than normal distribution, it is planned to use standard nonparametric tests: Mann–Whitney U test, Wilcoxon T test for dependent samples, and Friedman test for dependent samples.

Comparison of the frequencies of indicators between treatment groups will be carried out using Pearson's chi-square test if the number of points in each cell of the crosstab is ≥ 5 , or Fisher's exact test if at least one of the crosstab cells contains < 5 points.

In the event that any of the initial data reveal the incomparability of the study groups (statistically significant differences in demographic and other initial data between the groups), an analysis of the parameters of efficacy and safety will be additionally carried out together with the primary planned analysis using multivariate statistics (ANCOVA or logistic regression depending on the type of parameter under study), adjusted for the initial indicator(s), according to which the groups initially differed.

6. Concomitant therapy

6.1. Permitted concomitant therapy

Oral beta-lactam antibiotic (for example, amoxicillin, amoxicillin + clavulanic acid, cefixime, etc.) (see Background Antibacterial Therapy) as per inclusion criterion No. 3, in the same dosage regimen as at the study initiation.

Medicinal products for the treatment of comorbidities that were used prior to registration without violating any non-inclusion criteria. Female patients that take oral contraceptives may continue taking them during the study.

STATISTICAL ANALYSIS PLAN

Standard symptomatic treatment agents used to treat acute respiratory infections (in case of medical need), including anilides, triazole derivatives, with the exception of medicinal products that can have a laxative effect (for example, throat lozenges with sugar substitutes).

Agents for relieving symptoms of acute diarrhea (in case of medical need), including electrolyte solutions, with the exception of sorbents.

The prescription of therapy for acute diarrhea and symptomatic therapy for acute respiratory infections is possible only by the decision of the investigator.

6.2. Prohibited concomitant therapy

1. Systemic glucocorticosteroids within the last 8 weeks prior to and during the study;
2. Any antibacterial agents in the last 3 months before the study and during the study, with the exception of antibacterial medicinal products provided for in inclusion criterion No. 3 during the study;
3. The use of any proton pump inhibitors within 3 months prior to the study;
4. Other probiotics (bacteria or yeast, medicinal products, food supplements, fermented products) and Broncho-munal[®] within 2 weeks prior to and during the study;

Any therapy (including medicinal products, medical devices, and dietary supplements) that may affect stool consistency, in the opinion of the investigator, shall not be used within 14 days prior to Visit 1 (with the exception of the medicinal products specified in items 3 and 4 of the Permitted Concomitant Therapy section).

Pharmacotherapeutic groups	Active substance
Systemic glucocorticosteroids	Hydrocortisone, cortisone, prednisolone, methylprednisolone, prednisone, triamcinolone, dexamethasone, betamethasone and their analogs, and/or combinations and derivatives
Antibacterial agents	Aminoglycosides, amphenicols, ansamycins, glycopeptides, carbapenems, lincosamides, macrolides and azalides, penicillins,

STATISTICAL ANALYSIS PLAN

	tetracyclines, cephalosporins – as monotherapy and/or combinations
Probiotics, incl. dietary supplements	Lactobacillus acidophilus, kefir fungi, Bifidobacterium bifidum, Escherichia coli, lactobacillus, lysozyme, Enterococcus faecium, Bifidobacterium longum, Bifidobacterium animalis, lactulose, Lactobacillus plantarum, Broncho-munal [®] – as monotherapy and as part of a medicinal product/ dietary supplement in any combination
Adsorbents	Activated carbon, aluminum oxide, attapulгите, colloidal silicon dioxide, lactulose, hydrolytic lignin, povidone, polymethylsiloxane polyhydrate, dioctahedral smectite – as monotherapy and as part of a medicinal product/ dietary supplement in any combination
Calcium products	Calcium glubionate, calcium lactobionate, calcium carbonate, calcium lactogluconate – as monotherapy and as part of a medicinal product/ dietary supplement in any combination
Antidiarrheal medicinal products	Attapulгите, Bergenia rhizoma, Bacillus subtilis, Bifidobacterium bifidum, Snakeweed rhizoma, burnet rhizomes with roots, loperamide + simethicone, loperamide, plantain oval seed coat, Racecadotril, Dioctahedral smectite, fruits of bird cherry, fruits of common blueberries – as monotherapy and as part of a medicinal product/ dietary supplement in any combination

Myotropic antispasmodics	Bendazole, metamizole, papaverine, drotaverine, theobromine, bencyclan, darifenacin, dicycloverine, codeine, camilofin, mecloxamine, propyphenazone, ergotamine, mebeverine, oxybutynin, otilonium bromide, platyphylline, pinaverium bromide, trimebutine as well as herbal antispasmodics – as monotherapy and as part of a medicinal product/ dietary supplement in any combination
Antiemetics and medicinal products affecting gastrointestinal motility	Pyridostigmine, neostigmine, itopride, cisapride, aprepitant, bromopride, granisetron, dimenhydrinate, domperidone, levomenthol solution in menthyl isovalerate, meclozine, moxastine, ondansetron, palonosetron, perphenazine, thiethylperazine, trifluoperazine, tropisetron, fosaprepitant as well as herbal medicinal products – as monotherapy and as part of a medicinal product/ dietary supplement in any combination

7. Efficacy analysis

Analysis of efficacy endpoints will be carried out in accordance with Section V of the Recommendations of the Board of the Eurasian Economic Commission *On Guidelines on the Principles of Applying Biostatistics in Clinical Trials of Medicines* No. 19 dated November 3, 2020. The main analysis tool will be the *R* programming language, version 3.7.

7.1. Primary endpoint analysis

Assessment of the incidence of AAD from Day 1 to the last day of the course of LRG-002 use vs. placebo in ARD patients receiving standard antimicrobial therapy. The primary efficacy criterion will be considered met if the odds ratio for AAD between the two groups is statistically significantly greater than 1 (i.e., the incidence of AAD in the LRG-002 group is lower than in the placebo group).

STATISTICAL ANALYSIS PLAN

The primary efficacy endpoint will be analyzed using a fixed-factor logistic regression model for the treatment group and age group. The treatment effect will be displayed using the adjusted odds ratio and the corresponding two-sided 95% confidence interval.

PCT will be calculated using the following set of functions of the R language:

- `glm` – building a logistic regression model;
- `summary` – displays the regression coefficients with an indication of the statistical significance;
- `confint` – displays confidence intervals for regression coefficients.

An example of a planned way of using these functions is shown in Figure 2. In the figure, the *Outcome* variable encodes the outcome (AAD – yes/no), *Treatment* encodes belonging to a particular study group, the *Age* variable encodes the age category (over or under 50 years old). The *p*-value is highlighted in red, the two-sided confidence interval is highlighted in blue, according to which the decision on reaching the PCT will be made.

```
> model_out <- glm(Outcome ~ Treatment + Age, data = df, family = "binomial")
> summary (model_out)
Call:
glm(formula = Outcome ~ Treatment + Age, family = "binomial", data = df)
Deviance Residuals:
    Min       1Q   Median       3Q      Max
-0.3327 -0.3327 -0.1635 -0.1635  2.9402

Coefficients:
            Estimate Std. Error z value Pr(>|z|)
(Intercept)  -4.3090    0.5949  -7.243 4.4e-13***
Treatment2    1.4427    0.6520   2.213 0.0269*
Ageage >=50  -0.5368    0.6558  -0.819 0.4130
```

```
Signif. codes: 0 '****' 0.001 '**' 0.01 '*' 0.05 '.' 0.1 ' ' 1

(Dispersion parameter for binomial family taken to be 1)

Null deviance: 135.35 on 509 degrees of freedom Residual deviance: 128.52 on
507 degrees of freedom
AIC: 134.52

Number of Fisher Scoring iterations: 7

> confint(model_out)
Waiting for profiling to be done...
      2.5%      97.5%
(Intercept) -5.7259968 -3.3150721
Treatment2  0.2808742  2.9311963
Age >=50    -2.0306660  0.6338301
```

Figure 2. Running functions for calculating PCT

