## **10. Statistic**

### **10.1 Description of statistical methods to be used, including the timing of each planned interim analysis**

Statistical analysis will be carried out using specialized R Project software.

All continuous (quantitative) indicators will be presented in the form of the following parameters of descriptive statistics:

- Number of observations;
- Arithmetic mean;
- 95% confidence interval of the mean;
- Standard deviation;
- Median;
- Interquartile range;
- Minimal;
- Maximum.

All sequential, categorical and qualitative indicators will be presented in the form of the following parameters of descriptive statistics:

- Absolute frequency (number of observations);
- Relative frequency (%);
- 95% CI for proportion.

All performed types of statistical analysis will be identical with respect to the investigational medicinal product LRG-002 and in the placebo group.

Concomitant diseases and AEs will be encoded using the MedDRA terms.

This section briefly describes the planned analysis. A complete analysis will be described in terms of statistical analysis.

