### **10.1.2 Primary efficacy parameter analysis**

Primary efficacy endpoint:

Evaluation of AAD incidence from the first to the last day of LRG-002 administration vs placebo in patients with ARDs, receiving standard antimicrobial therapy. The primary efficacy criterion will be considered achieved if the odds ratio for the AAD incidence between two groups is significantly higher than 1 (i.e. AAD incidence in the LRG-002 group is lower than in placebo group).

*AAD is defined as diarrhea associated with the AB use caused by C. difficile or of otherwise not identified etiology, upon analysis of stool samples and differential diagnostics according to investigator's judgment.*

*Diarrhea is defined as loose or watery stool (Type 5-7 according to Bristol Stool Form Scale) three times a day (frequent bowel movements with formed stool is not considered as diarrhea) in accordance with WHO criteria; based on the diary data (BSFS) and confirmation of AAD by the investigator.*

Each patient will be assessed only once, even if more than one AAD episode occurs in one patient.

The primary efficacy endpoint will be analyzed using a logistic regression model with fixed factors for the treatment group and age group. Treatment exposure will be displayed using the adjusted odds ratio and the corresponding bilateral 95% confidence interval. If necessary, an absolute risk difference will be presented with the bilateral 95% confidence interval and the amount needed for treatment. No central effects are expected in this study. Therefore, the center will not be added to the primary analysis model. However, the central effects will be studied in further sensitivity analysis and subgroups analysis. Additional sensitivity analyzes can be identified in terms of statistical analysis.

The p value for testing the adjusted equality of the equivalence of the odds ratio to 1 will be compared with a significance level of 0.05.

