3.1. Clinical and statistical significance

All the statistical tests within this study will be performed at 95% confidence level (threshold value p to confirm statistical significance is less than 0.05). The two-sided statistical criteria will be used for all other studied parameters.

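### Does SAP 7.1 leave open whether the p-value or the confidence interval decides the primary endpoint, and on which scale?

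*SAP*

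**What the plan says.** SAP 7.1 calls the endpoint met if the "odds ratio for AAD between the two groups is statistically significantly greater than 1", and explains that this means less AAD on LRG-002 than on placebo. The model is a logistic regression on treatment and age group. On reporting it says: "The treatment effect will be displayed using the adjusted odds ratio and the corresponding two-sided 95% confidence interval".

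Three R functions are listed. `glm` fits the model; `summary` "displays the regression coefficients with an indication of the statistical significance"; `confint` "displays confidence intervals for regression coefficients". Figure 2, offered as an example of how these functions will be used, prints a treatment coefficient of 1.4427 (SE 0.6520, z 2.213, p 0.0269) and an interval of 0.2808742 to 2.9311963. The text introducing the figure mentions the p-value in red, then adds that "the two-sided confidence interval is highlighted in blue, according to which the decision on reaching the PCT will be made".

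The decision rule also appears in two other places. In Protocol 10.1.2 the p-value for "testing the adjusted equality of the equivalence of the odds ratio to 1 will be compared with a significance level of 0.05". In SAP 3.1 the "threshold value p to confirm statistical significance is less than 0.05", for all tests in the study.

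**The concern.** Two things look wrong on a first reading of SAP 7.1.

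**Which output decides.** The clause follows both a p-value and an interval, and grammatically it attaches most easily to the interval. The two are not restatements of each other: `summary` gives a Wald test, while `confint` on a `glm` object profiles the likelihood. A trial could have p just above 0.05 with an interval that excludes no effect. If the plan really left the choice open, it could be made after seeing the result.

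**Which scale.** The criterion is an OR compared with 1, but the listed code stops at coefficients. The printed interval contains 1, although it shows a significant effect because the no-effect value for a coefficient is 0. Nothing listed turns it into the OR interval that the same section promises.

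At stake would be an ambiguous success rule for the only confirmatory test in the trial.

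**Working it through.** **Inputs.** AAD rates 0.26 (placebo) and 0.15 (LRG-002), two-sided alpha 0.05, power 80%, 208 per group for analysis and 260 per group randomized (SAP 2.3). Coefficient, SE, interval and deviances from Figure 2 (SAP 7.1).

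**1. The plan's sample size reproduces.** n = ((1.960 + 0.842)/0.11)² × (0.15×0.85 + 0.26×0.74) = 207.5, so 208. With 20% withdrawal, 208/0.8 = 260. The planned OR, placebo against LRG-002, is (0.26×0.85)/(0.15×0.74) = 1.99.

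**2. The two outputs are different tests.** 1.4427/0.6520 = 2.213, two-sided p = 0.0269: the printed p is Wald. A Wald interval would be 1.4427 ± 1.96×0.6520 = 0.165 to 2.721. The printed interval, 0.281 to 2.931, is not that, and the R message about profiling confirms profile likelihood.

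**3. Scale.** exp(1.4427) = 4.23; exp(0.2808742) = 1.32; exp(2.9311963) = 18.75. Figure 2 therefore corresponds to OR 4.23, 95% CI 1.32 to 18.75. A coefficient above 0 and an OR above 1 are the same statement, and `summary` already tests the coefficient against 0. The p-value is unaffected by the scale.

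**4. How often the outputs disagree at the planned rates.** Two calculations were made: exact enumeration of all 2×2 tables without age, and 200,000 simulated trials per setting with the treatment-plus-age model. The simulation assumed no age effect and a share aged 50 or over of 29% or 50%, which the documents do not give.

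| 0.26 vs 0.15 | Power by Wald p | Power by profile CI | Disagree |
|---|---|---|---|
| 208/arm, exact, unadjusted | 79.9% | 80.0% | 0.16% |
| 260/arm, exact, unadjusted | 87.8% | 88.1% | 0.28% |
| 208/arm, simulated, with age | 79.9–80.0% | 80.3% | 0.34–0.35% |
| 260/arm, simulated, with age | 87.9% | 88.1–88.2% | 0.27–0.28% |

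Every disagreement had the profile interval significant and the Wald p not.

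**5. Dependence on the event rate (exact, unadjusted).** These rates are illustrative and not design values. The third row uses rates recovered from Figure 2: its null deviance of 135.35 on 510 records corresponds to 15 events, and a table of 3/257 and 12/253, with 75 patients aged 50 or over in each arm, reproduces the printed coefficients and standard errors.

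| Assumed rates | Disagree |
|---|---|
| 10% vs 5%, 260/arm | 1.9% |
| 5% vs 2%, 260/arm | 5.9% |
| 12/253 vs 3/257, 255/arm | 14.0% (10.9% with 253 and 257) |
| 3% in both arms, 255/arm | 2.3% (two-sided rejection 3.3% Wald, 5.5% profile) |

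**6. The texts side by side.** Protocol 10.1.2 names the p-value and 0.05. SAP 3.1 repeats the p threshold. SAP 7.1 assigns statistical significance to `summary`, whose p-value is the one highlighted. Only the final clause of that sentence can be read otherwise, and it can equally be read as covering both highlighted outputs.

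**The case for a change.** The strongest case for a change is that the near-agreement in step 4 holds only if AAD is as common as assumed. With few events the outputs part company in more than one trial in ten, and at 3% in both arms the Wald test is conservative while the profile interval slightly exceeds 5%. A success rule ought to name one output before the data are seen. The Protocol also hands the detail to the SAP ("A complete analysis will be described in terms of statistical analysis"), so one could argue that the SAP's clause prevails. Finally, the SAP does not say which arm is level 2 of the treatment variable, so the exponentiated coefficient could be the reciprocal of the intended OR.

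Part of this stands. The clause is loosely worded, and the event-rate dependence is real. But it does not leave the rule open. Protocol 10.7 asks that departures from its statistical plan be listed and justified, and the SAP text lists none here, so the p-value rule carries over. SAP 7.1 also says in words which direction counts as success, and the Protocol synopsis gives the comparison as placebo against LRG-002. An analyst must orient the OR that way whatever the factor coding. Replacing the clause with one that keeps a Wald p beside a profile interval would leave the same possible mismatch in the tables, so it would gain little.

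**Conclusion.** No change to the plan is needed. The deciding statistic is the p-value for treatment against 0.05, set by Protocol 10.1.2 and SAP 3.1 and produced by `summary`. The interval accompanies the estimate. Reporting it as an OR is already a commitment in SAP 7.1, and the conversion is a routine step that an example figure need not show. What remains is an awkward clause that a competent analyst reads correctly.

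At the planned rates even the other reading would alter the conclusion in fewer than 0.4% of trials and move power by about 0.3 percentage points or less. That size rests on the 26% and 15% assumptions and, for the age-adjusted figures, on no age effect and an assumed age split. If AAD proves much rarer, the outputs will differ more often. The answer is still the p-value, because the rule does not depend on the event rate.

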7.2. Analysis of secondary endpoints

The whole secondary efficiency analysis will be considered investigational, therefore multiplicity correction will not be performed; for test results, no formal capacity calculation will be provided.

Secondary efficiency points are classified into three groups:

1. Points characterizing the likelihood of a particular clinically significant event:
 - The occurrence rate of any diarrhea in the treatment group as compared to the placebo group;
 - The occurrence rate of C. difficile-associated AAD in the treatment group as compared to the placebo group;
 - The incidence of AAD not associated with C. difficile in the treatment group as compared to the placebo group;

- Frequency of gastrointestinal symptoms, including nausea, vomiting, flatulence, abdominal pain, and decreased appetite (according to the diary data), in the treatment group as compared to the placebo group;
- Number (share) of patients using standard symptomatic therapy to relieve symptoms of acute diarrhea in the treatment group as compared to the placebo group;
- The hospitalization rate in the treatment group as compared to the placebo group.

For these types of BKT, contingency tables 2×2 will be generated where the rows will show the groups, the columns will show the facts of the presence or absence of a particular event, the elements of the table are the patients included in the analysis. The contingency table data will be analyzed using Fisher's test (using the `fisher.test` function) or the chi-square test (using the `chisq.test` function) depending on the number of observations per cell (< 5 or ≥ 5).

2. Points characterizing the severity (or duration) of a particular clinical manifestation:

- Occurrence of bowel movements per day (according to the diary data) in the treatment group as compared to the placebo group;
- Duration of AAD (the time from the onset of AAD to the normalization of stool form according to BSS (types 1, 2, 3, and 4) and the presence of normal stool within 48 hours)) in the treatment group as compared to the placebo group;
- Duration of any diarrhea (time from diarrhea onset to normalization of stool form according to BSS (type 1, 2, 3, and 4) and presence of normal stool for 48 hours) in the treatment group as compared to the placebo group;
- Severity of the gastrointestinal symptoms, including nausea, vomiting, flatulence, abdominal pain, and decreased appetite (according to the diary data);
- A number of days of using symptomatic therapy to relieve symptoms of acute diarrhea in the treatment group as compared to the placebo group.

Due to the obvious difference between the distribution of these indicators from the normal (they have a discrete distribution), the nonparametric Mann–Whitney–Wilcoxon test implemented in the `wilcox.test` function will be used for intergroup comparison.

3. Other secondary endpoints:

- Weight change at Visit 3 compared with Visit 1 in the placebo group as compared to the treatment group. This BKT can have a distribution close to normal. Accordingly, at the first stage, the normality of the distribution will be assessed (using the Shapiro–Wilk test implemented in the shapiro.test function), at the second stage, either the t-test (t.test function) or the Mann–Whitney–Wilcoxon test (wilcox.test function) will be used.
- Stool consistency change (according to Bristol Stool Scale) (according to the diary) in the treatment group as compared to the placebo group; any individual changes in stool consistency will be classified as improved/unchanged/worsened, and the difference between the groups will be analyzed using chi-square criterion (chisq.test function).

8. Safety analysis

Safety parameters will be evaluated at every planned or unscheduled visit.

The safety assessment will be based on the following indicators (between Visits 1 and 3) compared between the investigational medicinal product and placebo:

- Changes in the vital signs over time and the incidence of pathological abnormalities revealed during the physical examination will be summarized by the group; a comparison will be made between the groups using appropriate tests for quantitative and qualitative data.

The data will be checked for compliance with the normal distribution law using the Shapiro–Wilk test.

Intergroup comparison of secondary endpoints related to quantitative scales will be performed using Student's t-test for independent samples if the data correspond to the normal distribution law; otherwise, the Mann–Whitney U test will be applied to independent samples.

Intergroup comparisons of secondary endpoints related to categorical scales will be performed using Pearson's chi-square test if the number of points in each cell of the crosstab is ≥ 5 , or Fisher's exact test if at least one of the crosstab cells contains < 5 points.

The dynamics will be assessed using ANOVA methods with repeated measurements if the data correspond to the normal distribution, otherwise, the Friedman test will be applied.

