The consideration of AAD studies for LGG from [16], concerning infections in adults (including *H. pylori*), gives 0.14 for a probiotic group and 0.22 for a control group.

Combining all the strains, we obtain an incidence of 0.26 for the placebo and 0.15 for the probiotic group.

The following indicators were used for calculations:

1. The difference of absolute risks of AAD in the placebo group and the treatment group is expected to be positive.

The incidence of AAD = 0.26 is assumed for the placebo and 0.15 for the treatment group.

Possibility of type I error: 0.05

Power of the study is 80%, which corresponds to the type II error: 0.20.

Statistical hypothesis is the evidence of superior efficacy:

$$H_0: OR = 1$$

$$H_1: OR \neq 1,$$

where OR is the odds ratio between both groups.

The ratio between the treatment and placebo group sizes is 1:1.

Amount of the patient in each group could be calculated using the following formula [2]:

$$n_T = n_R = \left(\frac{Z_{1-\alpha/2} + Z_\beta}{p_T - p_R} \right)^2 [p_T(1-p_T) + p_R(1-p_R)] = 208$$

Thus, the minimum number of patients required for statistical analysis is 416 (208 patients per group). Taking into account a 20% withdrawal rate, one needs to randomize 520 subjects (260 patients per group).

3. General analysis values

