4.1. Patient distribution

It will be a double-blind, randomized study.

Patients will be included by applying stratified randomization in two strata:

Age < 50 years

Age ≥ 50 years

Each treatment group will be balanced as 1:1 in each stratum.

Stratified randomization is a two-stage procedure in which patients who enter a clinical study are first grouped into strata. Within each stratum, patients are then assigned to treatment according to separate randomization schedules. The randomization module of EDC system assigns patient unique randomization code based on a treatment group and stratum. Randomization schedules will be hidden from medical personnel and all other persons involved in the study (monitors, data management, biometry, sponsor, etc.), except for the specialists responsible for IMP labeling and emergency unblinding.

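### Secondary efficacy analyses leave out the randomisation stratum (age) and commit to no between-group estimate with a confidence interval: a small, inexpensive improvement to SAP 7.2

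*SAP*

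**What the plan says.** **Design and primary analysis.** SAP 4.1 stratifies randomisation by age below 50 and age 50 or over: "Each treatment group will be balanced as 1:1 in each stratum". SAP 7.1 analyses the primary endpoint "using a fixed-factor logistic regression model for the treatment group and age group" and reports an adjusted odds ratio with a two-sided 95% CI. Figure 2 shows the R call.

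**Secondary analyses (SAP 7.2).**
- Event endpoints (any diarrhea, *C. difficile* and non-*C. difficile* AAD, GI symptoms, use of symptomatic therapy, hospitalisation): 2×2 tables in which "the rows will show the groups, the columns will show the facts of the presence or absence of a particular event", tested with `fisher.test` or `chisq.test`.
- Severity, count and duration endpoints: the Mann–Whitney–Wilcoxon test in the `wilcox.test` "function will be used for intergroup comparison".
- Weight change: `t.test` or `wilcox.test`, chosen after a Shapiro–Wilk test.
- Stool consistency (improved, unchanged, worsened): `chisq.test`.

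None uses age. Protocol 10.1.3 is also unadjusted. Both documents call the secondary analyses investigational, with no multiplicity correction and no power calculation.

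**Reporting.** In SAP Appendix 1, the group-comparison shell for quantitative variables (Table 2) has only p-value rows. The categorical shell (Table 4) has counts, percentages and a Fisher p-value. Protocol 10.1 lists 95% CIs for means and proportions as descriptive statistics, which describe each arm and not the difference.

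**Conditional adjustment.** SAP 5 and Protocol 10.1.1 add an ANCOVA or logistic analysis if a baseline variable differs significantly between arms.

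**The concern.** Balanced allocation within age strata removes the between-stratum component from the sampling variance of the treatment difference. An unstratified test still counts that component in its standard error. If age predicts the outcome, the test rejects too rarely under the null and loses a little power.

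The second issue is separate and concerns reporting. Uncorrected p-values from analyses labelled investigational carry little confirmatory weight; what a reader can use is an estimate with its interval. The contrast is sharpest for AAD. The primary endpoint gets an age-adjusted odds ratio with CI, while the *C. difficile* and non-*C. difficile* components get unadjusted tests and no promised estimate, so the whole and its parts cannot be read on one scale.

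**Working it through.** **1. The plan's own figure.** SAP 2.3 gives the inputs: "Possibility of type I error: 0.05"; "Power of the study is 80%, which corresponds to the type II error: 0.20"; "The incidence of AAD = 0.26 is assumed for the placebo and 0.15 for the treatment group". SAP 3.1 makes the tests two-sided. The unpooled formula gives

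n = (1.960 + 0.842)² × (0.26×0.74 + 0.15×0.85) / 0.11² = 207.51, rounded up to 208 per arm; 208/0.80 = 260 randomised.

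This matches the SAP. No such figure exists for any secondary endpoint.

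**2. What is not given.** Neither document states the share of patients aged ≥50 or the effect of age on any endpoint. I therefore assume ranges: share s = 20–50%, age odds ratio 1 to 5.

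**3. Binary endpoint at the protocol's rates (208 per arm).** Hold the marginal rates at 0.26 and 0.15 and let w be the stratum shares.

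- Unstratified variance: V_u = [p_P(1−p_P) + p_T(1−p_T)]/n
- Stratified variance: V_s = Σ w_k[p_Pk(1−p_Pk) + p_Tk(1−p_Tk)]/n

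Example: s = 0.35, age OR 3. Stratum rates are 0.1833 and 0.4024 (placebo), 0.0982 and 0.2462 (LRG-002).

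n·V_s = 0.65×(0.1497 + 0.0886) + 0.35×(0.2405 + 0.1856) = 0.3040, against n·V_u = 0.1924 + 0.1275 = 0.3199. The variance ratio is 0.950 and the SE ratio 0.975.

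Power uses the pooled null variance (V_0u or V_0s): Φ[(0.11 − 1.96√V_0)/√V_s]. The true size of the unstratified test is 2[1 − Φ(1.96√(V_0u/V_0s))].

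| Age OR | SE ratio (s = 20–50%) | Power, unstratified | Power, stratified | Size of unstratified test |
|---|---|---|---|---|
| 1 | 1.000 | 79.6% | 79.6% | 5.0% |
| 2 | 0.990–0.992 | 79.8% | 80.2–80.3% | 4.8% |
| 3 | 0.975–0.979 | 80.1–80.2% | 81.2–81.5% | 4.5–4.6% |
| 5 | 0.946–0.955 | 80.7–80.9% | 83.0–83.6% | 3.9–4.1% |

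**4. A more frequent secondary endpoint.** Assume any diarrhea at 30% vs 20%, 260 per arm, 30% aged ≥50. Simulation (200,000 trials per scenario, fixed 1:1 within strata) of the age-stratified CMH test against the uncorrected chi-square test:

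| Age OR | Power gain from stratifying | Size of unstratified test |
|---|---|---|
| 1 | about 0 | 5.1% |
| 2 | +0.4 points | 4.8% |
| 3 | +1.5 points | 4.5% |
| 5 | +3.4 points | 3.7% |

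**5. The function actually named.** `chisq.test` with default options applies a continuity correction to a 2×2 table. Exact enumeration for the same 260 per arm, 30% vs 20% and no age effect gives 75.5% power uncorrected and 72.0% corrected, a loss of about 3.5 points. At 25% in both arms the corrected size is 3.9%. This loss has nothing to do with age. Together the two effects put the default test 3.2, 3.9, 5.0 and 7.1 points below the stratified test at age OR 1, 2, 3 and 5.

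**6. Other endpoint types.**
- Rare event (assumed 2% vs 1%, 260 per arm, 35% aged ≥50): variance ratio 0.998 to 0.990 for age OR 2 to 5.
- Continuous: SE ratio = √(1 − R²), with R² = s(1−s)δ²/[1 + s(1−s)δ²] and δ the age difference in SD. This gives 0.995–0.997 at δ = 0.2 and 0.970–0.981 at δ = 0.5.

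**7. What the R functions return.** `fisher.test` on 54/208 vs 31/208 returns OR 2.00 (95% CI 1.19–3.39). `t.test` returns both means and a CI for the difference. `chisq.test` and default `wilcox.test` return neither an estimate nor a CI.

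**The case against.** The strongest reply is that nothing here can mislead. The unstratified tests hold their level, the analyses are declared investigational, and at an age odds ratio of 2 the power at stake is about half a point. The documents offer no evidence of a large age effect; the age coefficient in Figure 2 belongs to a worked example and says nothing about this trial. All of that stands, and it sets the weight of the point.

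Three stronger readings are tempting, and the documents do not support them.
- *The planned tests give p-values only.* Not for `fisher.test` or `t.test`, and arm-level CIs are planned in Protocol 10.1. The supportable statement is that no between-group estimate is committed to in SAP 7.2 or shown in the Appendix 1 shells.
- *The missing estimates make the analysis less precise.* They do not; that is a reporting gap. Any precision loss comes from omitting age, and it is zero if age is not prognostic.
- *The omission biases the tests or inflates false positives.* The error runs the other way.

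One might also say the conditional adjustment in SAP 5 covers this. It does not: it needs a significant baseline difference, which stratified allocation makes unlikely for age.

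**Conclusion.** The point holds as a minor, nearly free improvement. Every secondary efficacy endpoint in SAP 7.2 is tested without the stratum used in randomisation and in the primary model, and no treatment difference with a CI is promised for any of them. The tests are valid. The age-related loss runs from nil (age not prognostic) through about half a point of power (age OR 2) to about 2 to 3.5 points (age OR 5). Those figures rest on assumed stratum shares and age effects, and in the second scenario on assumed event rates. The default continuity correction is a separate loss of about 3.5 points in that scenario, and is as large as or larger than the age effect over the range examined. No confirmatory conclusion depends on this; the main gain is secondary results that can be read alongside the primary one.

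**What to change.** In SAP 7.2:
- **Binary endpoints:** `glm(Outcome ~ Treatment + Age, family = "binomial")`, as in Figure 2, reporting the odds ratio and risk difference with 95% CIs. Use an exact age-stratified test if events are very few. This also removes the continuity correction.
- **Counts, durations and severity:** an age-stratified Wilcoxon (van Elteren) test with an estimate and 95% CI. Where zeros dominate, such as days of symptomatic therapy, use a difference in means or a probability of superiority. A Hodges–Lehmann shift would be uninformative there: with most patients at zero in both arms it is zero.
- **Weight change:** a linear model with treatment and age stratum, reporting the adjusted mean difference and 95% CI.
- **Stool consistency:** an age-stratified CMH test.

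Add estimate and CI columns to the group-comparison shells in Appendix 1.

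Cost: SAP wording, revised shells and modest coding, with the binary code already written. There is no change to design, sample size or data collection. Because Protocol 10.1.3 is also unadjusted, the change must be listed and justified as Protocol 10.7 requires.
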